Primary Outcome Measures:	Retrospective and prospective data will be collected, that include: Overall participant survival, evaluated based on chronological age at time of death or at conclusion of study, whichever occurs first.
Secondary Outcome Measures:	Retrospective and prospective data will be collected, that include: The rate of change (i.e., slope) in neurocognitive functioning over the duration of follow-up will be determined; and will also be compared to available published natural history data. This analysis will be conducted separately for each of the two disease sub-types: infantile and juvenile. The primary neurocognitive measure for both pediatric groups is age-equivalent scores of the Bayley Scales of Infant and Toddler Development for expressive communication, receptive communication, fine motor skills and gross motor skills. The secondary neurocognitive measure for both pediatric groups is standard and age-equivalent scores of the Vineland Adaptive Behavior Scales for communication, daily living skills, socialization and motor skills, and the Vineland composite standard score.
Statistical Considerations (sample size and analysis plan):	The sample size (number of enrolled subjects) will be large enough to detect trends and differences. The primary analysis for Syner-G therapy will use the intention-to-treat (ITT) population and evaluate overall survival based on chronological patient age. Median survival will be compared to previously reported natural history studies of infantile and juvenile gangliosidoses. For rate of change in neurocognitive functioning over the duration of follow-up, using general estimating equations (GEE) and an exchangeable working correlation structure, variance estimation for confidence intervals and p-values will take into account the possible correlated nature of multiple measurements on the same individual. Supportive analyses will include evaluation using the per-protocol (PP) population. Subgroup analyses: analyses will be repeated separately among the infantile and juvenile forms of both GM1 and GM2 gangliosidosis.
Sponsors (federal, state, foundation and industry support):	National Institutes of Health (NIH)

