12.0 Study Objectives

12.1 Primary objective. The primary analysis for Syner-G treatment regimen will use the intention-to-treat (ITT) population and evaluate overall survival. This will be evaluated based on chronological age at time of death or conclusion of study (whichever occurs first), and compared to available natural history data. Median survival will be compared to previously reported natural history studies of infantile⁹ and juvenile¹¹ forms. Median survival of patients with infantile GM2 gangliosidosis was estimated at 47 months based on data from the National Tay-Sachs and Allied Diseases database for patients born after 2000.⁹ Median survival for the juvenile form was estimated at 14.5 years.¹¹

12.2 Secondary objective. Evaluate the effect of Syner-G therapy in patients with infant and juvenile gangliosidoses on changes in neurodevelopmental status, as assessed using age-equivalent scores of the Bayley Scales of Infant and Toddler Development for expressive communication, receptive communication, fine motor skills and gross motor skills; and using the Vineland Adaptive Behavior Scales.

A secondary endpoint will be the rate of change (i.e., slope) in neurocognitive functioning over the duration of follow-up, compared to available natural history data. This analysis will be conducted separately for each of the two sub-types: infantile and juvenile. The primary neurocognitive functioning endpoint for both pediatric groups is age-equivalent scores of the Bayley Scales of Infant and Toddler Development for expressive communication, receptive communication, fine motor skills and gross motor skills. Another primary neurocognitive functioning endpoint for both pediatric groups is age-equivalent scores of the Vineland Adaptive Behavior Scales. Using general estimating equations (GEE) and an exchangeable working correlation structure, variance estimation for confidence intervals and P-values will take into

account the possible correlated nature of multiple measurements on the same individual. Supportive analyses will include evaluation using the per-protocol (PP) population.

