13.2 Study population. Study population will be any patient with an infantile or late-infantile/juvenile gangliosidosis disease.

13.3 Sample size. A total of 30 infants or children:

- 5 patients with infantile Tay-Sachs disease
- 5 patients with juvenile Tay-Sachs disease
- 5 patients with infantile Sandhoff disease
- 5 patients with juvenile Sandhoff disease
- 5 patients with infantile GM1 gangliosidosis
- 5 patients with juvenile GM1 gangliosidosis

13.4 Subject recruitment. Subjects will be recruited from the investigators' clinical practice and through the Lysosomal Disease Network. This clinical trial will be posted on ClinicalTrials.gov and this may serve to recruit patients to the study.

13.5 Subject screening. Eligibility will be assessed during a baseline evaluation and will include confirmation of gangliosidosis disease via mutation analysis and tissue (e.g. leukocyte) ascertainment of level of hexosaminidase or β -galactosidase enzyme activity.

13.6 Prior and concomitant therapy. Subjects may have had previous therapies for gangliosidosis. If subjects are taking miglustat and/or pyrimethamine, and/or are on a ketogenic diet at the time of screening, they will be allowed to continue these therapies and will be allowed to participate in the Syner-G study.

13.7 Inclusion criteria. Subjects will be eligible to participate in the study if all of the following criteria are met: 1) confirmed diagnosis of infantile or juvenile GM1 or GM2 gangliosidosis via mutation analysis and tissue enzyme activity analysis (e.g. leukocyte activity of β -hexosaminidase A, including percent activity contributed from both α -subunit and β -subunits) or tissue β -galactosidase enzyme activity; 2) subjects must be age 0 - 17 years at time of enrollment; and 3) subjects and their caregivers must work closely with their University of Minnesota ketogenic diet team, and with their local ketogenic diet team, which must include a ketogenic dietician and a neurologist trained in the ketogenic diet.

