18.0 Data Analysis

18.1 Subject populations for analysis:

- Intention-to-treat Population (ITT): All subjects who initiate any portion of the treatment regimen in association with this study
- Per-protocol Population (PP): Includes all subjects who initiate treatment and are compliant with at least 75% of prescribed drug doses of miglustat, and at least 3:1 ketogenic diet.
- Safety population: All subjects who receive any amount of the combination treatment regimen. Due to the nature of a combination treatment, multiple groups may be identified, should partial adherence be observed.

18.2 Sample size determination. The sample size for the study was determined primarily by feasibility due to the extremely rare nature of the disease. There are two distinct sub-types to be evaluated: infantile and juvenile. Analysis will be based on variability estimates from published natural history studies^{8,11,19} of the infantile form and juvenile form, and correlation between baseline and annual follow-up for up to 4 years.

18.3 Statistical analysis. Descriptive analyses of baseline characteristics and outcomes will include means, standard deviations, medians, and ranges for continuous variables and frequencies for categorical variables. Treatment compliance for each group will also be evaluated. All analyses will be conducted separately for the two disease sub-types – infantile and juvenile – due to the highly heterogeneous patient groups.

The primary analysis for Syner-G treatment regimen will use the intention-to-treat (ITT) population and evaluate overall survival. This will be evaluated based on chronological age at time of death or conclusion of study (whichever occurs first), and compared to available natural history data. Median survival will be compared to previously reported natural history studies of infantile⁹ and juvenile¹¹ forms. Infantile median survival was estimated at 47 months based on data from the National Tay-Sachs and Allied Diseases database for patients born after 2000.⁹ Median survival for the juvenile form was estimated at 14.5 years.¹¹

A secondary endpoint will be the rate of change (i.e., slope) in neurocognitive functioning over the duration of follow-up, compared to available natural history data. This analysis will be conducted separately for each of the two sub-types: infantile and juvenile. The primary

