neurocognitive functioning endpoint for both pediatric groups is age-equivalent scores of the Bayley Scales of Infant and Toddler Development for expressive communication, receptive communication, fine motor skills and gross motor skills. Another primary neurocognitive functioning endpoint for both pediatric groups is age-equivalent scores of the Vineland Adaptive Behavior Scales. Using general estimating equations (GEE) and an exchangeable working correlation structure, variance estimation for confidence intervals and P-values will take into account the possible correlated nature of multiple measurements on the same individual. Supportive analyses will include evaluation using the per-protocol (PP) population.

Safety analyses will be primarily descriptive, reporting the number and percentage of AEs and descriptive summaries. These analyses will use multiple safety populations according to which components of the combination therapy subjects were exposed to. Due to the longitudinal nature of the study and potential for later-emerging effects, the safety profile will be characterized for each sub-type over time. Supportive analyses will include evaluation using the PP population.

Subgroup analyses: analyses will be repeated among GM1 gangliosidosis patients and among GM2 gangliosidosis patients, and among the infantile and juvenile forms of both GM1 and GM2 gangliosidosis.

18.4 Missing data. Despite best efforts to avoid missing data, it is possible that some will occur and will be a potential limitation to the interpretation and generalizability of results. In particular, missing data may arise for non-survival outcomes (e.g. neurocognitive function data) in the event of death. For these instances, it is unclear whether a complete-case analysis (i.e. excluding patients who die) would be unbiased, and therefore would be unsatisfactory. It is also unclear what would be an appropriate magnitude of discount to satisfactorily represent the negative outcome of death. By conducting both the complete-case analysis (unbiased if death is independent of the non-survival outcome) and an analysis with an imputed value for instances of death (intention-to-treat type of analysis), the potential magnitude of treatment effect will be better characterized.

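### The primary survival comparison sets an observed median beside a bare published median, with no interval, test or threshold for survival

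*Combined protocol and SAP*

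**What the plan says.** Section 18.3 makes overall survival in the intention-to-treat population the primary analysis, on the scale of chronological age at death or study end. The comparison is given in one sentence: "Median survival will be compared to previously reported natural history studies of infantile" and juvenile forms. The reference values follow as single numbers: "Infantile median survival was estimated at 47 months based on data" from a patient-association database, and, in section 12.1 as well, "Median survival for the juvenile form was estimated at 14.5 years". The Synopsis repeats it: "Median survival will be compared to previously reported natural history studies of infantile and juvenile gangliosidoses".

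Section 18.3 also states "All analyses will be conducted separately for the two disease sub-types", so there are two primary comparisons. Section 13.3 sets the size: "A total of 30 infants or children", in six cells of five.

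Inference is mentioned once in section 18.3, in the sentence on generalised estimating equations for the secondary neurocognitive slope: "variance estimation for confidence intervals and P-values will take into account the possible correlated nature of multiple measurements on the same individual". That concerns repeated measurements on a child, which survival does not have. For survival the documents name no estimator, interval, test, significance level, threshold or treatment of an unreached median.

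**The concern.** Read literally, the primary comparison has two inputs per sub-type: a sample median from about 15 children and a constant. Neither carries sampling error, although the plan itself describes both published medians as estimates. A comparison of that kind cannot separate benefit from chance.

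The stated aims are not purely descriptive. Section 8.1 wants to learn whether the combination improves overall survival, and the Synopsis says the sample is large enough to detect differences. Section 18.3 calls the safety analyses primarily descriptive but does not say so of survival. Nothing in the plan would stop a report from presenting a median a little above 47 months or 14.5 years as longer survival.

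**Working it through.** **Inputs.** Six cells of five give 6 × 5 = 30, which agrees with section 13.3. That is 15 per sub-type (10 GM2, 5 GM1). The benchmarks are 47 months and 14.5 years (sections 12.1 and 18.3). No significance level, power, effect size or event count is given for survival, so there is no operating figure to reproduce.

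**Step 1: ideal conditions.** Assume no effect, a true median equal to the benchmark, entry unrelated to survival, and complete follow-up. The median of 15 is the 8th ordered survival time. It exceeds the benchmark when at most 7 of 15 die before it:

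- Per sub-type: P(Bin(15, 0.5) ≤ 7) = 0.500.
- At least one of two independent sub-types: 1 − 0.5² = 0.75.

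**Step 2: conditions nearer this design.** Section 13.7 admits children aged 0–17 years, who must be alive to enrol, and the Synopsis gives a five-year study. The documents give no distribution of entry ages and no survival shape, so these are assumptions: Weibull survival with the benchmark as true median (shapes 2–4 infantile, 2–3 juvenile), follow-up of up to five years, 15 children, a Kaplan-Meier median by age, 2,000 runs per scenario, and an unreached median counted as longer. The chance that an ineffective regimen shows a longer median is:

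| Sub-type, assumed entry age | Entry age ignored | Risk set starts at entry age |
|---|---|---|
| Infantile, 6–18 months | 50–59% | 49–54% |
| Infantile, 6–36 months | 56–78% | 47–54% |
| Infantile, 12–48 months | 83–95% | 50–60% |
| Juvenile, 3–10 years | 65–79% | 56–65% |
| Juvenile, 3–17 years | 96–99% | 47–52% |

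Combining infantile entry at 6–36 months with juvenile entry at 3–10 years, and ignoring entry age, the chance in at least one sub-type runs from 1 − (1 − 0.5595)(1 − 0.648) = 0.845 to 1 − (1 − 0.779)(1 − 0.7855) = 0.953.

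The convention for an unreached median matters as much. For juvenile entry at 3–10 years the median is not reached in 63–79% of runs. If those runs are not counted as longer, the chance falls to 0–2%.

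**Step 3: a rule based on the lower confidence limit.** With complete data, the 4th and 12th of 15 ordered times form an interval for the median with coverage 1 − 2 × 0.0176 = 96.5%. Requiring the 4th to exceed the benchmark means at least 12 of 15 outlive it:

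- False benefit per sub-type: P(Bin(15, 0.5) ≤ 3) = (1 + 15 + 105 + 455)/32,768 = 0.0176.
- In at least one of two: 1 − (1 − 0.0176)² = 0.035.
- Power: at hazard ratio h, a child outlives the benchmark with probability 0.5^h. For h = 0.50, 0.33 and 0.25 that is 0.707, 0.796 and 0.841, giving P(at least 12 of 15) = 32%, 63% and 79%.

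**Step 4: the same rule with entry age ignored.** In null simulations with assumed entry ages and 1–5 years of follow-up, counting a limit that could not be estimated as above the benchmark, the lower-limit rule gave false benefit in about 1–8% of infantile and 20–24% of juvenile runs. A one-sample log-rank test adjusted for entry age stayed at or below about 2%. An interval alone is therefore not enough; entry age must be handled too.

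**The case against.** The strongest objection is that the plan contains no success rule. It says survival will be evaluated and compared; it does not say that a higher median counts as benefit, and the word compared does not exclude an interval. This stands. A reader might infer that the trial has adopted a decision rule with a 50% or 75% error rate. The documents do not support that: the figures describe what follows if any excess is read as benefit. What remains is that the only comparison on the page is point against point.

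Section 18.2 says analysis will use variability estimates from published natural history studies, and one of the three references is the juvenile survival source. That could be read as covering survival. But the infantile survival source is not among the three, and the same sentence speaks of correlation between baseline and annual follow-up, which fits the repeated scores. At best it is ambiguous.

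It is also fair that 50% and 75% rest on ideal conditions that this design does not meet. Step 2 shows the chance is usually higher, but it can be far lower if an unreached median is not counted as longer.

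Finally, this is a single-arm phase II study in very rare diseases, sized by feasibility. Descriptive reporting would be legitimate, but the plan should then say so.

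**Conclusion.** The point holds as an omission in the primary analysis: survival has no interval, test or threshold, while the secondary slope has inference. If any excess over the published median is read as benefit, an ineffective regimen shows it 50% of the time per sub-type and 75% of the time in at least one. This assumes 15 children per sub-type, independent sub-types, unbiased entry, complete follow-up and an exact benchmark. With delayed entry ignored and an unreached median counted as longer, the chance is usually higher; how much higher depends on entry ages that the documents do not give.

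Two further inferences should be avoided. A reader might conclude that the GM1/GM2 repeats make some favourable median nearly inevitable. The documents label these as subgroup analyses and attach no primary conclusion to them. Sections 1.1.4 and 12.1 trace the benchmarks to GM2 studies, and no GM1 median is given to score GM1 children against. A reader might also take 1.8% and 3.5% as the error rates this trial would have under a lower-limit rule. They apply only to complete data with unbiased entry.

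**What to change.** In section 18.3, and to match in section 12.1 and the Synopsis:

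- Estimate survival by age for each sub-type, with each child entering the risk set at age of enrolment, and report the median with its 95% confidence interval.
- Conclude longer survival only if an estimable lower limit exceeds the benchmark. If a published reference curve is available, a one-sample log-rank test that counts expected deaths from entry age, at one-sided 2.5%, may be used instead. The documents themselves give only the two medians.
- Call the result inconclusive when the interval includes the benchmark or the limit cannot be estimated.
- Report the benchmark's own uncertainty, and label the GM1/GM2 repeats descriptive.

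Alternatively, state that the survival comparison is descriptive, report the interval, and draw no conclusion of benefit from the median alone.

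The cost is analysis-plan wording and standard methods on data already to be collected, with no added patients or procedures. The downside is that many results will be inconclusive with about 15 children per sub-type: power is about 32% at a hazard ratio of 0.50 and 79% at 0.25, even with full follow-up.

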13.0 Study Design

13.1 Overview of study design. Both retrospective and prospective data will be collected during this study. This is a single-arm treatment protocol, with intention-to-treat per-protocol design. The primary analysis for Syner-G treatment regimen will use the intention-to-treat (ITT) population and evaluate overall survival. This will be evaluated based on chronological age at time of death or conclusion of study (whichever occurs first), and compared to available natural history data. This will be conducted separately for each of the two sub-types: infantile and juvenile. The neurocognitive functioning endpoint for both groups is the cognition domain of the Bayley Scales of Infant and Toddler Development for expressive communication, receptive communication, fine motor skills, gross motor skills; and the Vineland Adaptive Behavior Scales. Each of the other 4 domains will be evaluated as secondary endpoints. Using general estimating equations (GEE) and an exchangeable working correlation structure, variance estimation for confidence intervals and P-values will take into account the possible correlated nature of multiple measurements on the same individual. Supportive analyses will include evaluation using the per-protocol (PP) population.

Subgroup analyses: analyses will be repeated among GM1 gangliosidosis patients and among GM2 gangliosidosis patients, and among the infantile and juvenile forms of both GM1 and GM2 gangliosidosis.

Yearly evaluations, whenever possible, will also explore changes in seizure frequency and severity, and in movement disorders, evaluated by neurologist and parent-report.

Some subjects do not have insurance coverage for certain evaluations. Sometimes the insurance coverage changes and clinical care that was covered in the past is no longer covered. The investigators will continue to see these patients annually, whenever possible, and will provide the scheduled clinical-care visits according to what is allowed within the restrictions of the subject's health care insurance. When any given subject is unable to make their annual visit to the University of Minnesota due to illness or weakness, this will not cause them to be withdrawn from the research study. The reason for foregoing the evaluation will be documented in the subject's file, and the investigators will continue to follow them through telephone contacts with family members and health care providers.

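### Slope intervals and P-values come from exchangeable GEE on about 15 patients per sub-type (5 to 20 in subgroups) with no small-sample correction; run as ordinary GEE, the intervals are too narrow

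*Combined protocol and SAP*

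**What the plan says.** Section 18.3 makes the rate of change in neurocognitive functioning a secondary endpoint and describes its inference in one sentence: "Using general estimating equations (GEE) and an exchangeable working correlation structure, variance estimation for confidence intervals and P-values" are to reflect the correlation between measurements on one child. The Synopsis (Statistical Considerations) and sections 12.2 and 13.1 repeat this, for example "using general estimating equations (GEE) and an exchangeable working correlation structure" in the Synopsis. None of them says whether the errors are robust or model-based, whether the reference is normal or t, or how few patients are allowed for.

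On the size of the fits, section 18.3 states that "All analyses will be conducted separately for the two disease sub-types", and gives as the reason "due to the highly heterogeneous patient groups". Section 13.3 plans six cells of 5 patients. For subgroups, the Synopsis says "analyses will be repeated separately among the infantile and juvenile forms of both GM1 and GM2 gangliosidosis". Sections 13.1 and 18.3 add fits pooled over form: "analyses will be repeated among GM1 gangliosidosis patients and among GM2 gangliosidosis patients".

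**The concern.** The sandwich variance is justified when the number of independent clusters is large. Here the clusters are children, and there are 15 or fewer in every fit except pooled GM2, which has 20. The uncorrected sandwich uses residuals that the fit has already shrunk, so it understates the variance. A normal reference then ignores that the variance is itself estimated from a handful of children. Both errors make the interval too short and the P-value too small.

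This inference is all the plan offers on neurodevelopmental benefit, and the error runs towards false precision. It is largest in the 5-patient GM1 subgroups. Because the estimator is not named, it could also be chosen after the data are seen.

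**Working it through.** **Cluster counts** (section 13.3, six cells of 5; total 6 × 5 = 30, as the plan states)

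- Infantile or juvenile: 3 × 5 = 15 each
- GM2 pooled: 4 × 5 = 20; GM1 pooled: 2 × 5 = 10
- Infantile or juvenile GM2: 2 × 5 = 10 each; infantile or juvenile GM1: 5 each

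The plan states no power, precision or confidence level. A two-sided 95% level is assumed throughout.

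**Exact result with equal visits.** The exchangeable-GEE slope is then the mean of the n per-child slopes. Let s² be their sample variance.

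- Uncorrected sandwich: variance = ((n−1)/n) · s²/n. Non-coverage with a normal reference = P(|t(n−1)| > 1.96·√((n−1)/n)), for normally distributed per-child slopes.
- Mancl-DeRouen: variance = (n/(n−1)) · s²/n. Non-coverage with t(n−1) = P(|t(n−1)| > t.975·√(n/(n−1))).
- Width ratio of corrected to ordinary = (t.975/1.96) · n/(n−1).

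At n = 15, t.975 = 2.145. The ordinary cut-off is 1.96 × √(14/15) = 1.894, so P(|t(14)| > 1.894) = 7.9%. The width ratio is (2.145/1.96) × (15/14) = 1.17.

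| n | Ordinary GEE misses | Mancl-DeRouen with t misses | Widening |
|---|---|---|---|
| 20 | 7.1% | 4.5% | 12% |
| 15 | 7.9% | 4.3% | 17% |
| 10 | 9.6% | 4.1% | 28% |
| 5 | 15.4% | 3.6% | 77% |

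These figures do not depend on the SDs or on the number of visits.

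**Unequal visits (simulation).** The Synopsis plans rolling enrollment over five years, and section 17.0 expects missed annual visits, so equal visits are the favourable case. The simulation used 6,000 runs per setting (standard error about 0.3 points near 5%) and 64 settings. There were five assessments, following "correlation between baseline and annual follow-up for up to 4 years" in section 18.2. Assumed, with no basis in the documents: intercept SD 6 and residual SD 2 in age-equivalent months; slope SD 0, 0.5, 2 or 4 months per year; and the visit patterns. Non-coverage of ordinary GEE:

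| Visit pattern | n=20 | n=15 | n=10 | n=5 |
|---|---|---|---|---|
| 70% attendance | 7-8% | 8-9% | 9-11% | 16-18% |
| 2-5 visits | 8-10% | 10-12% | 12-17% | 20-29% |
| 1-5 visits | 10-12% | 11-15% | 14-20% | 23-36% |

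Mancl-DeRouen with t missed 3-7% across all 64 settings, with n counting only children who have at least two visits. If single-visit children are also counted, it missed 5-9% in the 1-5 visit pattern. A separate simulation with 25% loss per year and slope SD 0, 1.5 or 3 gave 12-15% at n = 15 and 23-36% at n = 5 for ordinary GEE. At n = 200 its coverage returned to 94-96.5%, so the shortfall is a small-sample effect.

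**After the planned LOCF** (section 18.4; assumed 20% or 40% drop-out after 2-4 of 5 visits; 8,000 runs per setting). Measured against the LOCF estimate's own mean, ordinary GEE missed 7-8%, 8-9%, 9-11% and 15-18% at n = 20, 15, 10 and 5. The corrected interval missed 3-6%. LOCF also biases the slope: an assumed −3 per year became −2.7 or −2.4, and −1 became −0.9 or −0.8. At n = 15 the corrected interval still missed the true slope in 4-46% of runs.

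**Model-based errors instead** (complete visits). They missed 3-5% with one common slope, 7-9% at slope SD 0.5 and 27-28% at slope SD 2. With slopes that vary between children this does not recover even at n = 200, because the exchangeable structure is then wrong.

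**The case against.** The plan never says it will use the uncorrected sandwich with a normal reference, so what is shown is an unspecified detail and not a stated error. That is true, and the concern is conditional for that reason. But the two ordinary ways of running the stated method both under-cover: the uncorrected sandwich at all of these sizes, and model-based errors unless visits are complete and slopes are common. The plan's own description of the patients as heterogeneous argues against common slopes.

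The 10-12% figure for the main fits assumes unequal visits, whereas the plan fills records by LOCF for loss to follow-up, where the figure is 8-9%. This is fair for loss to follow-up. LOCF need not cover intermittent missed visits, staggered entry or the complete-case analysis after death, so unequal visits remain likely. Their extent is not given in the documents.

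The schedule in section 17.0 allows up to six neuropsychological assessments, against five implied by section 18.2. The equal-visit figures do not change, and simulation with six gave the same range as with five: about 9-12% at n = 15 and 19-29% at n = 5.

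Finally, the endpoint is secondary with no decision rule, the sample size rests on feasibility, and LOCF bias can exceed the defect being fixed. All of this stands, and it limits the severity. It does not remove the case for a correction that costs one paragraph.

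**Conclusion.** The concern holds. As ordinary GEE, the main 15-patient fits would miss the true slope about 8% of the time with equal visits, and about 10-12% with 2-5 visits per child, against a nominal 5%. The 5-patient subgroups would miss about 15% and 20-29%.

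The equal-visit figures are exact for normally distributed per-child slopes. The unequal-visit figures depend on assumed SDs and visit patterns. All presume a 95% two-sided level. They cover small-sample variance only. They exclude LOCF bias, the value imputed for death, and uncertainty in the natural-history slope, for which section 1.1.3 acknowledges limited data. The change should be made, but it concerns a secondary endpoint and leaves the primary survival analysis untouched.

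**What to change.** Keep GEE. Add to section 18.3:

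> CIs and P-values use the Mancl-DeRouen bias-corrected sandwich variance with a t reference on n−1 degrees of freedom. n is the number of patients in that fit with at least two observed assessments; patients with one assessment stay in the fit but are not counted in n. This corrects small-sample variance only, not bias from LOCF or the value imputed for death, nor uncertainty in the natural-history slope.

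The Synopsis and sections 12.2 and 13.1 should refer to 18.3. It is worth adding that no interval is given when fewer than two patients in a fit have repeat assessments; this occurred in 0.7% of runs at n = 5 with 1-5 visits. The 5-patient GM1 subgroups could instead be reported descriptively.

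Another bias-corrected sandwich with t would also serve. Kauermann-Carroll is exact (5.0%) and narrower with equal visits, but misses 6-12% with 2-5 visits, against 4-7% for Mancl-DeRouen.

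The cost is one paragraph, three cross-references and wider intervals; the estimator is in standard software. With equal visits the widening is as tabulated above, and the correction is slightly conservative. With 2-5 visits, intervals widen by 17-19% (n = 20), 23-26% (n = 15), 39-44% (n = 10) and 112-128% (n = 5). At n = 5 with some single-visit children, the mean width is about four times as large. With unequal visits, non-coverage of up to about 7% remains.
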